7 SAFETY ASSESSMENTS

All participants will be monitored for safety and the emergence of adverse events. As detailed in Section 6.2.3, adverse events (**Form 09**) are queried and inventoried at all follow-up appointments. Of note, the *surgery is not the study intervention*—although adverse events encountered with surgery will be documented and followed. With respect to the actual study intervention, i.e., application of vaginal estrogen cream, these are the expected adverse experiences/toxicities documented in prior studies:

Minor side effects: vaginal itching (2-3%), breast tenderness (2-3%), vaginal discharge (6-11%)*, joint aches (7-9%)*, headache (10-13%)*.

Severe side effects: stroke (<1%), blood clots in the legs or lungs (<1%)

* = in clinical studies, the rates of these side-effects were comparable in patients treated with estrogen and placebo vaginal creams

If minor side effects such as those listed above are encountered early in the study (e.g., in the preoperative time period between baseline and surgery), the participant will be encouraged to try to continue the study medication with reassurance and as-needed therapies such as acetaminophen for management of headache or body aches or breast tenderness. Vaginal discharge—if related to *Candidiasis* or bacterial vaginosis—can be treated with oral medication as detailed in 5.3.1. Frequently, these minor side effects are found to be transient. If at any time these effects are more bothersome to the patient and persist despite attempts at management, the study medication will be discontinued, but the patient will continue to be monitored if she has not withdrawn from the study.

If severe side effects such as those listed above are encountered and thought possibly due to study medication, the study medication will be discontinued.

7.1 Specification of Safety Parameters

No particular safety measures or laboratory parameters are pre-specified to direct the investigators to discontinue the study medication in a participant.

7.2 Methods and Timing for Assessing, Recording, and Analyzing Safety Parameters

As detailed in Item 6.2.3, possible safety issues or adverse events (**Form 09**) are queried and inventoried at all follow-up appointments.

The actual risks of the intervention in this study, conjugated estrogen (CE) cream (i.e., Premarin cream), at the planned dose and frequency, are minor. In a well-done, large study comparing CE cream to placebo cream (Bachmann 2009, total n=423)⁶³ with 12mo follow-up, these adverse events were reported; there were no statistically significant differences between CE cream and placebo cream:

- vaginal discharge or leukorrhea: CE cream 6.1%, placebo 10.5%
- headache: CE cream 11.5%, placebo 12.8%
- arthralgia: CE cream 7.7%, placebo 8.3%
- any adverse event leading to drug discontinuation (12 wk): CE cream 3.5%, placebo 2.1%

In a different study comparing vaginal CE cream (also 0.625mg/1 g) to an oral synthetic estrogen (Botsis 1997, total n=72, 6mo follow-up)⁷⁹, these adverse events were reported; as above, they were not statistically different between treatment arms:

- vaginal itching: CE cream 2.8%, Synthetic PO estrogen: 2.8%
- breast tenderness: CE cream 2.8%, Synthetic PO estrogen: 2.8%

Finally, in another larger study comparing CE cream to placebo cream (Freedman 2009, total n=305, 12-wk follow-up)⁸⁰, ANY adverse event was reported in 55% of patients using CE cream and 47% using placebo cream, but AE's bothersome enough for withdrawal from the study occurred in just 3 of 150 (2%) CE cream patients and 2 of 155 (1.3%) placebo cream patients.

Risk of a *severe* side effect related to this dosing of CE cream (i.e., stroke, deep vein thrombosis, or pulmonary embolism) is less than 1%.

Although systemic absorption of vaginal estrogen has been documented, in this trial we will use low dosage vaginal CE cream (1g of 0.625mg/g cream) because this therapy does not involve significant increases in estrogen in blood and has been shown to have positive effects on postmenopausal vaginal atrophy. Women at high risk for potential adverse effects from systemic absorption of estrogen (specifically stroke, blood clots in the lungs or deep veins of the legs, or breast, ovarian or endometrial cancer) are excluded from study participation.

Any hypothetical adverse event involving endometrial pathology related to estrogen exposure (i.e., hyperplasia, cancer) is not applicable in this study as all participants will either be status-post hysterectomy or undergoing total vaginal hysterectomy at the time of the planned prolapse repair surgery.

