Design: Randomized, double-blind, placebo-controlled trial of pre- and postoperative intravaginal estrogen therapy in 222 postmenopausal women with symptomatic prolapse undergoing a standardized surgical repair using native tissue.

Primary outcome: prolapse recurrence as defined by a composite of objective prolapse beyond the hymen, subjective/symptomatic prolapse (feeling of a bulge or *no change* or *worse* on the patient's global impression of improvement), or retreatment (e.g., reoperation or pessary use) assessed 1 year postoperatively. *Time to failure* will be compared in the two groups.

Important secondary outcomes assessing for changes in overactive bladder and urinary incontinence symptoms will be made by comparing symptoms (validated questionnaires) from Baseline to Pre-op/time of surgery. Aim 3 (see above, histomorphology, connective tissue studies) will be assessed from full thickness anterior apical vaginal wall biopsies taken at the time of surgery.

Interventions and Duration

Intervention: 1g conjugated estrogen (CE) cream (Premarin®, Pfizer Inc.) given nightly for 2 weeks then twice-weekly to complete planned 6-8 weeks (5 weeks minimum) therapy before a standardized uterosacral or sacrospinous ligament suspension transvaginal prolapse repair surgery. Those with a uterus will undergo concomitant total vaginal hysterectomy first. Twice-weekly CE cream application is then resumed upon discharge and continued for 1 year postoperatively.

Comparator: placebo vaginal cream, same schedule

Duration: The primary outcome of prolapse recurrence is assessed at one year postoperatively with continued surveillance of participants until 3 years postoperatively.

Sample Size and Population

Total sample size: N=222; 111 per treatment group

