5.3 Concomitant Interventions

5.3.1 Allowed Interventions

- *Medications:* If vaginal discharge is encountered during the setting of study cream use, e.g. vaginal *Candidiasis* or bacterial vaginosis, appropriate treatment may be provided. For simplicity of not having to coordinate application of multiple vaginal creams (e.g., study cream and anti-fungal cream), oral treatments are preferred, e.g. diflucan or metronidazole pills for *Candidiasis* or bacterial vaginosis, respectively.
- *Surgical:* in addition to the required surgical intervention of uterosacral or sacrospinous ligament suspension (see 5.3.2), anterior/ posterior colporrhaphies, vaginal hysterectomy, and midurethral slings are allowed.

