6.2.4 Completion/Final Evaluation

See 36-month Postoperative Visit above.

At the completion of 36 months or at the participant’s final visit (if early withdrawal), “Final Status” documentation (**Form 20**) will be completed. This gives the following possible reasons for withdrawal: ineligible/ screen failure (few, if any, of these are anticipated); subject never began Study Cream; subject did not complete/undergo surgery; subject voluntarily withdrew from study (reason specified); investigator withdrew patient from study (reason specified); lost to follow-up; death; transition to long-term resident or skilled nursing facility; study termination; other (reason specified).

Possible reasons for early withdrawal by the subject may include intolerance of the study medication, patient preference, or inability to continue with follow-up examinations and assessments. Early withdrawal of the participant by the investigator may also be for participant’s inability to adhere to study medication or visits.

If a participant withdraws (or is withdrawn) after randomization but before 12 months postoperatively, there is a prompt to the research coordinator/ physician examiner to collect a final VMI specimen.

It is not anticipated that participants will need to continue to be monitored after study withdrawal and discontinuation of the study medication.

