9.2 Sample Size and Randomization

The literature reports failure by the above definition occurring in ~40% of patients with a native tissue USLS (i.e., ~60% “success”).⁶⁹ A 2-sided logrank test with an overall sample size of **188 subjects** (94 each group) achieves 80% power at a 0.05 significance level to detect a hazard ratio of 0.5188 when the proportion of those "surviving" (i.e. "successes") in the control group is **65% compared to 80%** in the treated group, **measured at 1 year**. This presumes the accrual pattern across the study time period (3 years of accrual) is uniform. This N=188 already accounts for **25%** either lost to follow-up *or non-adherent to study cream* in the control and treatment groups. Allowing for an additional **15% loss of participants** from baseline to surgery, **222 total participants** are needed.

Potential problems & alternatives:

Differences in baseline characteristics between the groups may occur by chance, but we will mitigate that risk by stratifying by clinical site, hysterectomy status, and duration since menopause (<10y & ≥10y).

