Aim 3 Outcomes: If there is 10% loss of patients from randomization (baseline) to surgery, there will still be 100 patients per arm eligible for the standardized intraoperative apical anterior vaginal wall surgical biopsy. Our pilot trial (Section 2.2a, *Humans*) indicates sufficient power to determine 2-fold differences in collagen subtypes and MMP activity using tissues from UTSW. Further, with ~42 samples from UTSW (21 in each group), this will provide 80% power to also detect 2-fold differences in LOX protein and mRNA expression. All Aim 3 outcomes of interest (e.g. histological wall thicknesses, qPCR-determined relative mRNA levels, collagen subtypes and elastic fiber content, collagenase and protease activity) will be summarized using the following statistics: mean, standard deviation, median, minimum and maximum. Additionally, because most biomarkers are not normally distributed, the geometric mean and standard deviation based on natural log transformed values will also be calculated. Summaries will be constructed by treatment group (CE vs. placebo) and comparisons conducted using 2-tailed Student’s *t*-tests comparing natural log transformed levels. Because this translational study (Aim 3) is considered to be descriptive and a relatively large number of markers are being considered, all p-values will be presented without adjustment for multiple comparisons and should be interpreted accordingly. We will correlate any treatment-group differences in vaginal wall or smooth muscle histomorphology, ERs, collagen gene expression, and protease downregulation with *clinical outcomes*, namely, objective or subjective “success” as outlined in Aims 1 and 2.

Ideally, CE cream application will support an improvement in prolapse recurrence success/failure rates 1y postop, but even if CE cream has a null or non-significant effect, the entire population will be divided into prolapse repair failures (*cases*) and successes (*controls*), and, controlling for CE cream exposure, univariate comparisons will be made of the continuous outcomes from Aim 3 (2-tailed Student’s *t*-tests). Those variables that attain a significance level of 0.1 or less in univariate analyses will be considered jointly in a multivariable backward stepwise logistic regression model. An accepted “rule of thumb”

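### Section 7.2 rules out endometrial adverse events because every woman will have had a hysterectomy, but the plan itself allows for women with a uterus who use cream and never reach surgery

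*Combined protocol and SAP*

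**What the plan says.** Section 7.2 sets aside estrogen-related hyperplasia and cancer of the endometrium: such an event "is not applicable in this study as all participants will either be status-post hysterectomy or undergoing total vaginal hysterectomy" at the planned repair.

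On hysterectomy, the Précis (Interventions and Duration) agrees: "Those with a uterus will undergo concomitant total vaginal hysterectomy first". Section 5.3.1 puts it among the permitted procedures: "vaginal hysterectomy, and midurethral slings are allowed". Section 3 (Standardization of surgical procedure) does the same. Section 5.3.2, which lists the required surgery, names only the ligament suspension.

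On who is exposed, Section 4.1 admits women who still have a uterus. Section 6.2.2 has the participant start cream the evening she obtains it, and the Précis plans 6-8 weeks of use before surgery. Section 9.2 enlarges the sample: "Allowing for an additional 15% loss of participants from baseline to surgery". Section 9.5 (Aim 3) uses another figure for the same interval: "If there is 10% loss of patients from randomization (baseline) to surgery". Section 6.2.4 lists not undergoing surgery as a reason for withdrawal.

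On safety capture, Section 7.3 records any adverse event whether or not it is related to treatment, and Sections 5.4 and 9.5 apply monitoring to everyone randomized who uses study drug. Section 6.2.3 makes abnormal surgical pathology at the 1-month visit a trigger for the adverse event form. The solicited list in Section 7.3 does not include vaginal bleeding. On follow-up, Section 6.2.4 states: "It is not anticipated that participants will need to continue to be monitored after study withdrawal". Section 8 asks women who withdraw to continue scheduled evaluations, and Section 7.4 runs serious event reporting to the drug supplier through 28 days after the last dose.

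**The concern.** A safety section should not declare a class of events impossible on a premise that the sample size section contradicts. A woman with a uterus who is randomized, uses cream for some weeks and then does not have the operation has been exposed and still has an endometrium. For her the reason given in Section 7.2 is false, and she produces no surgical specimen, so the pathology check cannot reach her.

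At stake is modest but real: how completely bleeding or endometrial findings are captured in a small exposed group, and whether the absence of such reports at the end of the trial can be read as absence of events. The primary outcome is not affected.

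**Working it through.** **Inputs.** N = 188 before pre-surgery loss (Section 9.2); 15% loss from baseline to surgery (Section 9.2); 10% loss over the same interval (Section 9.5); 222 randomized, 111 per arm (Précis).

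**Step 1, the plan's own totals.** 188 / (1 - 0.15) = 221.2, rounded up to 222. This reproduces the stated sample size. For Aim 3, 111 × 0.90 = 99.9, which reproduces the stated 100 per arm.

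**Step 2, women allowed for who do not reach surgery.**
- At 15%: 222 × 0.15 = 33.3 (or 222 - 188 = 34 from the rounded totals); 33.3 / 2 = 16.7 per arm.
- At 10%: 222 × 0.10 = 22.2; 22.2 / 2 = 11.1 per arm.

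**Step 3, those with a uterus, assigned to active cream.** The documents do not give the share with a uterus, so it is varied. The table also assumes that every such woman starts cream, which makes each entry an upper figure for its row.

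| Assumed share with a uterus | 15% loss | 10% loss |
|---|---|---|
| 25% | 16.65 × 0.25 = 4.2 | 11.1 × 0.25 = 2.8 |
| 50% | 8.3 | 5.6 |
| 75% | 12.5 | 8.3 |
| 100% | 16.7 | 11.1 |

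The range is about 3 to 17 women on active cream.

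**Step 4, is the allowance plausible?** In the pilot (Section 2.2a), 30 women planning a repair that involved hysterectomy were randomized and two per group had no surgery: 4 / 30 = 13%, between the two planning figures.

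**Step 5, which capture routes reach these women?**
- General adverse event recording (Sections 5.4, 7.3, 9.5): yes, while the woman is in follow-up.
- Solicited events (Section 7.3): no bleeding item is listed, although Section 4.2 treats unexplained genital bleeding as a contraindication at entry.
- Surgical pathology trigger (Section 6.2.3): operated women only.
- After withdrawal: Section 6.2.4 anticipates no need for monitoring, while Section 8 asks for continued evaluations and Section 7.4 covers serious events for 28 days after the last dose.

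**The case against.** The strongest reply is that Section 7.2 gives a risk rationale and does not exclude any data. Every unfavorable diagnosis, symptom or sign in a cream user is recordable, the forms have lines for other events, the preoperative visit asks about complaints related to the cream, and Section 7.4 sends adverse events to the DSMB by randomization group. This stands. A reader might infer that endometrial events would go unrecorded, and the documents do not support that. What is missing is a prompt, and the case report forms themselves are not in the documents.

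A reader might also infer that all 34 women will have been exposed. They may not be: the 15% is an enrolment allowance, Section 9.5 uses 10%, and Section 6.2.4 lists never starting cream as a separate reason for withdrawal.

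A third tempting reading is that the plan flatly contradicts itself on hysterectomy. The permitted-procedure lists cover a mixed population, some of whom no longer have a uterus, so listing hysterectomy as permitted need not mean that a woman may keep hers. The wording is ambiguous, and its absence from Section 5.3.2 leaves it unresolved.

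Finally, the pilot found no hyperplastic endometrium and no difference in endometrial thickness after six weeks of cream. This suggests a low expected risk, but the evidence is small and comes from surgical specimens, so it describes operated women. It does not make the premise in Section 7.2 true.

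**Conclusion.** The concern holds in a limited form. The premise that all participants have had or will have a hysterectomy is wrong as written, because the plan enrols women with a uterus, starts cream before surgery and allows for 10-15% loss before surgery. This leaves about 22 to 34 women overall and about 11 to 17 assigned to active cream. Of the latter, about 3 to 17 would have a uterus if the share is 25-100% and all start cream. Both of those shares are assumptions.

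The consequence is a gap in solicited capture for a small group that the pathology route cannot reach. General recording remains in place. The number of women concerned would be larger if hysterectomy proved optional at the repair, because cream continues for a year afterwards, but the documents do not establish that it is optional. This is a minor, inexpensive correction to the safety section.

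**What to change.** 1. In Section 7.2, limit the statement to women who have had a hysterectomy, and say how endometrial events are recorded in the others.
2. Reconcile the Précis and Section 7.2 with Sections 3, 5.3.1 and 5.3.2 on whether hysterectomy is required in women with a uterus. Which rule applies is for the investigators.
3. Reconcile Section 6.2.4 with Sections 7.4 and 8 on follow-up after withdrawal, so that the period over which events are collected in unoperated women is clear.
4. Add vaginal bleeding, and any endometrial finding that comes to light, as a solicited item on the existing adverse event form (Form 09) for women with a uterus who have used study cream. Report it by arm, with the number of such women as the denominator.

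The cost is one form item, a line in the safety tables and the wording changes. No new procedure or visit is needed, and no clinical rule is proposed. A solicited item will not detect silent endometrial change, since the plan schedules no endometrial assessment in unoperated women. Its value is in making reports of bleeding systematic and comparable between arms.

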7.3 Adverse Events and Serious Adverse Events

Definitions:

- An **adverse event (AE)** is defined as any unfavorable and unintended diagnosis, symptom, sign (including an abnormal laboratory finding), syndrome or disease which either occurs during the study, having been absent at baseline, or if present at baseline, appears to worsen. Adverse events will be recorded regardless of their relationship to the study intervention (**Form 09**).
- A **serious adverse event (SAE)** is defined as any untoward medical occurrence that results in death, is life threatening, requires inpatient hospitalization or prolongation of existing hospitalization, results in persistent or significant disability/incapacity, or is a congenital anomaly (**Form 09b**).

No pre-specified laboratory measures will be collected to assess safety.

These AE's will be collected as *solicited events* (**Forms 09, 12, 13, 14, 15**):

- Vaginal or vulvar complaints possibly associated with vaginal estrogen cream: itching, irritation, vaginal or vulvar rash, yeast infection or other discharge.
- Non-vaginal complaints anticipated with the use of vaginal estrogen cream: breast tenderness, joint aches, headache.
- Intraoperative AE's: bladder perforation, ureteral injury, urethral injury, rectal injury, other bowel injury, major vascular injury, anesthesia-related complications.
- AE's encountered during hospitalization after surgery: blood transfusion, wound complications, febrile or dermatologic complications, organ damage complications, cardiovascular complications, pulmonary complications, gastrointestinal complications, neurological complications, other.
- AE's encountered or reported at postoperative visits: vaginal or vulvar complaints (as above)/ non-vaginal complaints (as above) possibly related to estrogen

application, wound complications, febrile or dermatologic complications, neurological complications, other.

Case report forms (**Forms 09, 13, 14, 15**) all offer lines for data entry for “other” events, and Form 09 gives a reminder as to events triggering a SAE designation (**Form 09b**).

Possible safety issues or adverse events are queried and inventoried at all follow-up appointments and calls.

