7.4 Reporting Procedures

Each clinical investigator is responsible for reporting serious or unexpected adverse events to the IRB at their institution and to the Safety Monitor. The Safety Monitor/Officer (currently DSMB Chair, [name]), DCC Biostatistician (currently [name]), and NIA Project Scientist or Program Officer are notified by email when a report of any serious adverse event is entered into the REDCap database. The Safety Monitor summarizes the case; if it is potentially related to the intervention, the Safety Monitor reports it to the NIA Program Officer and the remaining DSMB members in an expedited manner (i.e., within 24 hours of learning of these events). The Safety Monitor (currently [name]) will determine whether the case should be reported to the IRBs at all the institutions participating in the trial. The DCC summarizes all SAE’s, including those that are definitely not related to the intervention, for the DSMB at each DSMB meeting.

Approximately every 6 months, or more frequently upon request of the Chair of the DSMB, the DCC will summarize all adverse events (including serious, unexpected and expected) by randomization group in a report to the DSMB. In addition, the report will contain accrual and drop-out rates. The DSMB will summarize their findings to the NIA with approval to continue the clinical trial, or a recommendation to modify the trial or terminate the trial.

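### Leg and lung clots, a named severe risk of the cream, are not solicited by name or category at the Pre-op or postoperative visits, and a clot treated without admission need not follow the expedited reporting route

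*Combined protocol and SAP*

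**What the plan says.** Section 7 lists the cream's side effects with the words "these are the expected adverse experiences/toxicities documented in prior studies". The severe ones are stroke and clots in the legs or lungs, each given as under 1%. Section 5.1 repeats the list. Section 7.2 names stroke, deep vein thrombosis and pulmonary embolism and puts the risk of a severe side effect at under 1%.

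Section 7.3 then sets out the solicited events:

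- Cream-related items are vaginal and vulvar complaints, plus "Non-vaginal complaints anticipated with the use of vaginal estrogen cream: breast tenderness, joint aches, headache".
- For the hospital stay after surgery, the list includes "organ damage complications, cardiovascular complications, pulmonary complications, gastrointestinal complications, neurological complications, other".
- For the postoperative visits, the list repeats the cream-related complaints and ends with "application, wound complications, febrile or dermatologic complications, neurological complications, other".

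The SAE definition in Section 7.3 covers death, threat to life, an event that "requires inpatient hospitalization or prolongation of existing hospitalization", lasting or significant disability, and congenital anomaly. Under Section 7.4, the Safety Monitor, the DCC biostatistician and NIA "are notified by email when a report of any serious adverse event is entered into the REDCap database". An SAE potentially related to the intervention goes on to NIA and the rest of the DSMB within 24 hours. All adverse events are summarised for the DSMB about every six months, or more often if its Chair asks.

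**The concern.** A solicited list exists so that the events that matter most do not depend on what a participant thinks to mention. Here the visit lists ask by name about headache, joint aches and itching, but leave clots, one of the two severe risks attributed to the drug, to open questions. The cream is used for several weeks before surgery and for a year afterwards, so most of the exposure lies outside the hospital stay, the only period with cardiovascular and pulmonary categories.

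The reporting rule adds to this. Whether a clot reaches the Safety Monitor promptly can turn on whether the woman was admitted, and that may vary with local practice rather than with the importance of the event. What is at stake is the completeness of the by-arm clot count and the speed with which the DSMB hears of a case. The primary outcome is not affected.

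**Working it through.** The plan states no figure on this point, so there is none to reproduce. The check is textual, followed by an illustration of scale.

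**Step 1. The two lists in Section 7.3 side by side.**

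| Category | Hospital stay | Postoperative visits |
|---|---|---|
| Transfusion | yes | no |
| Wound | yes | yes |
| Febrile or dermatologic | yes | yes |
| Organ damage | yes | no |
| Cardiovascular | yes | no |
| Pulmonary | yes | no |
| Gastrointestinal | yes | no |
| Neurological | yes | yes |
| Other | yes | yes |
| Cream-related complaints | not listed | yes |

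Stroke keeps a category at the visits (neurological). A leg or lung clot has none. The cream-related items, which are what the Pre-op visit has to draw on, do not include it.

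**Step 2. What can still catch a clot.**

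- Section 7.3 says adverse events are queried at every appointment and call, and that Forms 09, 13, 14 and 15 have lines for other events. Form 12 (Pre-op) is not among these, but Section 6.2.3 has it ask about complaints or complications of the cream, and Form 09 is available as needed.
- Form 15 takes interval medical history.
- The call script (footnote to Table 1) asks about new medical problems, hospital and emergency visits, and any change in medication. The 3- and 9-month calls fall within the year of cream use.
- The medication review (Form 05) is described at Baseline as covering incontinence and overactive-bladder drugs, so as described it would not pick up a new anticoagulant.

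**Step 3. A clot treated without admission, traced through the reporting rules.**

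1. Is it serious? Only if judged life threatening or disabling. Section 7.3 has no criterion for important medical events and no list of events always treated as serious.
2. Is it unexpected? The investigator's duty in Section 7.4 also covers unexpected events, but Section 7 lists clots among the expected ones.
3. If neither, the e-mail alert, the 24-hour report and the supplier report do not apply, since each starts from an SAE.
4. What remains is the roughly six-monthly DSMB report. Section 9.3 also gives severe adverse events as an example of what might prompt a safety review, with no deadline.

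**Step 4. Scale, for illustration.** Inputs: 111 women per arm (Précis) and an assumed cumulative clot risk p. The documents say only that it is under 1%. Expected clots are 111 × p. The chance of at least one is 1 − (1 − p)^111.

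| Assumed p | Expected clots | Chance of at least one |
|---|---|---|
| 0.1% | 0.11 | 1 − 0.999^111 = 10.5% |
| 0.5% | 0.56 | 1 − 0.995^111 = 42.7% |
| 1% | 1.11 | 1 − 0.99^111 = 67.2% |

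With the 94 per arm that Section 9.2 expects to reach surgery, the chances are 9.0%, 37.6% and 61.1%. The 1% row is a ceiling: Section 7.2 can be read as putting stroke and clots together below 1%. All rows count any clot, at any time and however treated.

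**The case against.** The best reply is that little would be lost in practice. Adverse events are asked about at every contact, 'other' lines exist, and the calls ask directly about emergency visits and medication changes, one of which a treated clot would probably bring up. Form 09 carries a reminder of what makes an event serious. Section 7 stops the cream for a severe side effect thought possibly due to it, whether or not it is labelled an SAE. Section 9.3 lets severe events prompt a review, and the DSMB Chair can ask for earlier reports. The forms and the Manual of Procedures are not in the documents and may contain more specific prompts.

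Most of this stands, and it rules out several stronger readings that a reader might infer:

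- *Clots would go uncollected.* Not supported. They can be recorded, but only through general questions.
- *A clot treated without admission cannot be an SAE.* Not supported. A lung clot, or a disabling leg clot, can meet the definition without admission.
- *Stroke is left out in the same way.* Not supported for the postoperative visits, where the neurological category covers it.
- *Such a clot is shut out of prompt review.* Not supported. Section 9.3 allows one, though it neither requires it nor sets a time.

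The reply does not remove the mismatch. An event that Section 7 treats as grave enough to stop the cream has no category at the visits and, if judged non-serious, no stated prompt route to the DSMB.

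**Conclusion.** The point holds as a gap in solicitation and in reporting. Clots are not solicited by name or category at the Pre-op or postoperative visits. One treated without admission, and not judged life threatening or disabling, need not follow the Section 7.4 route.

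The size is modest. At assumed clot risks of 0.1% to 1%, 0.1 to 1.1 clots of any kind are expected in the active arm. A reader might take the 10% to 67% as the chance that a clot is missed or reported late. It is not: that would require a clot outside the hospital stay that is also unprompted or unflagged, a smaller share that the documents do not allow one to compute. Nor can it be said that one missed case would change the safety conclusion. Section 9.3 sets no formal safety threshold, and about one event per arm supports no between-arm conclusion. Setting 24 hours against six months as a measured delay would also mislead, because the 24 hours run from the Safety Monitor's learning of a potentially related SAE, not from the event.

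The conclusion rests on the protocol text alone and assumes that the unseen forms follow the lists in Section 7.3. The change is worth making because it is cheap and concerns a named severe risk of the drug.

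**What to change.** In Section 7.3:

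1. Add venous thromboembolism (leg or lung clot) as a named solicited item on Form 12 (Pre-op), Form 15 (postoperative visits) and Form 18 (calls).
2. Name stroke explicitly under the existing neurological heading.
3. State that any deep vein thrombosis, pulmonary embolism or stroke is filed on Form 09b and follows the Section 7.4 route whether or not the woman is admitted.

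Sections 7, 7.3, 7.4 and 9.3 should then be read together so that they describe one route for these events. If the forms in the Manual of Procedures already carry such items, only the text of Section 7.3 needs to change.

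The cost is a few tick-boxes, one sentence on filing and perhaps a few extra expedited reports over the trial. Treatment, sample size and the primary analysis are untouched.
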